PART B STUDY DESCRIPTION

TITLE OF PROTOCOL	Seizure-like Hippocampal Activity in Alzheimer's Disease Neurodegeneration		
Principal Investigator	[name].		
Co-Investigators	[name]; [name]; [name]		
Mailing Address	[name]		
E-Mail Address	[contact]		
P.I.'s Telephone	[name]	P.I.'s Pager [name]	Fax: [name]
Sponsor/Funding Source	Fidelity Biosciences Research Initiative; Neurology Department internal funding		

B1. PURPOSE OF PROTOCOL

To test the hypothesis that increased hippocampal perfusion on arterial spin labeling MRI in patients with Alzheimer's Disease (AD) is partially driven by focal epileptiform activity, and that this abnormal activity contributes to memory dysfunction.

Here we propose applying an imaging technique, arterial spin labeling MRI (ASL-MRI), ideally suited for testing this hypothesis. We will utilize a pharmacological probe, levetiracetam, to test whether sub-clinical epileptiform activity is driving increases in hippocampal perfusion and contributing to the declarative memory impairment in AD. Levetiracetam is an antiepileptic drug (AED) that inhibits epileptiform activity. Levetiracetam inhibits burst firing without affecting normal neuronal excitability. We will study patients with mild AD in three sessions, counterbalanced for order, in a crossover design. In each session, participants will undergo a baseline electroencephalogram (EEG). They will then be given either a placebo or intravenous levetiracetam low dose (2.5 mg/kg) or high dose (7.5 mg/kg). After drug administration, repeat EEG, ASL-MRI perfusion imaging, and behavioral testing will be conducted. Participants will return at 1-2 week intervals for the second and third sessions in the other conditions (levetiracetam low dose / levetiracetam high dose / placebo). This study will test whether increased hippocampal perfusion in AD is caused by epileptiform activity, whether this activity is contributing to memory impairment, and whether antiepileptic medications might be a new avenue of treatment in AD. If validated, ASL-MRI would be an ideal tool to non-invasively determine whether antiepileptic medications are effective in decreasing aberrant excitatory activity in the hippocampus in AD.

Aim 1: To determine whether increased hippocampal perfusion in AD is caused by epileptiform activity.

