- h. 20 minutes before each dose of study drug, and at 10, 20, and 30 minutes after start of intravenous infusion of study drug: Systolic and diastolic blood pressure, heart rate, and respiratory rate
- i. Physical exam: appearance, cardiovascular, lung/chest, abdomen, extremities, and musculoskeletal.
- j. Neurological exam: mental status, cranial nerves, motor system, sensory system, reflexes, coordination, stance, gait
- k. Mini-Mental Status Examination
- l. Electroencephalogram

A 21-electrode array (Fp1, Fp2, F3, F4, C3, C4, P3, P4, O1, O2, F7, F8, T3, T4, T5, T6, Fz, Cz, Pz, reference, ground) of gold disc electrodes will be placed using paste technique, with electrode positions determined by the 10-20 International System.

Additional electrodes will be placed to monitor eye movements (superior and inferior to outer canthus of each eye) and electrocardiogram. EEG will be sampled at 250 Hz and band-pass filtered from 0.1-70Hz. EEG will be recorded for 20 minutes before, 20 minutes during, and 20 minutes after administration of study drug. During each 20 minute session, EEG will be recorded for 5 minutes with eyes open and 15 minutes resting with eyes closed. EEG will be analyzed using both visual and quantitative techniques ⁴⁴⁻⁴⁶. EEG will be visually inspected to determine 1) whether baseline epileptiform activity is present and is altered by study drug, and 2) whether study drug has other effects on EEG (such as diffuse slowing), which might affect the results of cognitive testing. Automated artifact detection and artifact decontamination filters will be used to minimize contributions of eye movements and other artifact sources. Data

segments containing possible artifacts will be excluded from analysis. For each session, EEG measures will include alpha peak power, beta band power, and delta/theta band power. will be determined for each session.

m. Study drug administration

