Participants will undergo declarative memory testing with the Free and Cued Selective Reminding Test, a task that is particularly sensitive to hippocampal function ⁴⁸. In addition, a short battery will be administered to test executive function, naming, visuospatial ability and semantic function (Trail Making Test Parts A+B, Phonemic fluency Test, Boston Naming Test 15-item version, clock drawing, category fluency). The primary endpoint for memory testing will be the free recall score from the Free and Cued Selective Reminding Test. This battery is fairly brief (30 min) but sensitive to both hippocampal function and changes in other cognitive realms impaired in AD.

p. Adverse events observed by investigator or reported spontaneously by the subject

6. Study Plan

The following assessments and procedures will be done at each study visit:

a. Screening visit

1. Informed consent
2. Demographics and baseline characteristics
3. Medical history
4. Neurologic history
5. Recent and concomitant medications
6. Blood collection for blood urea nitrogen and creatinine)
7. Vital signs: Systolic and diastolic blood pressure, heart rate, and respiratory rate; weight
8. Physical exam
9. Neurological exam
10. Mini-Mental Status Examination

b. Visits #1-3 (identical procedures, visit length 5-7 hours)

1. Vital signs: Systolic and diastolic blood pressure, heart rate, and respiratory rate; weight
2. Physical exam
3. Neurological exam
4. IV catheter placement
5. EEG (60 minute recording)
6. Study drug infusion (20 minutes)
7. Vital signs at 10, 20, 30 minutes after infusion
8. Imaging paradigm (60 minutes)
9. Behavioral testing (60-90 minutes)
10. Adverse events

There will be scheduled breaks between tests and scheduled lunch

c. Telephone follow-up

1. Follow up for adverse effects

B. Statistical Considerations

Sample Size Justification:

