The Principal Investigator will obtain informed consent from all subjects up to one week prior to their participation in this study. The consent form describes the study and provides sufficient information for subjects to make an informed decision about their participation in this study. The principal investigator or his designee will discuss the study with the subject. Patients with mild AD (MMSE \geq 20) are able to understand a consent form and over 95% can supply true consent (Buckles et. al, Neurology 2003). Participants will be reminded at the start of each session that they may discontinue at any time and that this will not affect their care in any way. In addition, we will engage a health care proxy, spouse, or close family member, where available. The subject will be given time to read the consent form and to ask questions. Upon entry into the study, the subject or surrogate will receive a copy of the consent form, and a copy will be filed with their study binder.

B7. STUDY LOCATION

Privacy

The subjects' privacy will be protected by ensuring that the conditions under which information will be collected afford protections against interactions with participants being witnessed, overheard or inadvertently intercepted or viewed. Furthermore, the information being collected will be minimized to include only the data necessary to accomplish the research.

A unique identifier code will be assigned to each subject. All information, including EEG data files, will be stripped of personal identifying information. Patient confidentiality will be strictly maintained, and results of all testing will be available only to subjects and/or their health care providers, if requested by the subjects.

Physical Setting

Study sessions will in the Clinical Research Center on the East Campus of BIDMC. MRI scans will be conducted in the Research Radiology department in an adjoining building (Rabb Building). Drug administration will take place at the Clinical Research Center and the Research Pharmacy will be responsible for counterbalancing.

B8. DATA SECURITY

Information about study subjects will be kept confidential and managed according to the requirements of the Health Insurance Portability and Accountability Act of 1996 (HIPAA). Those regulations require a signed subject authorization informing the subject of the following:

- What protected health information (PHI) will be collected from subjects in this study
- Who will have access to that information and why

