- Who will use or disclose that information
- The rights of a research subject to revoke their authorization for use of their PHI.

In the event that a subject revokes authorization to collect or use PHI, the investigator, by regulation, retains the ability to use all information collected prior to the revocation of subject authorization.

Subject binders will be kept in a locked cabinet accessible only to the investigators. For data analysis, data will be entered into a password-protected computerized database behind the BIDMC firewall. The investigator will retain study essential documents for at least 2 years after completion of the study.

General Safety

All safety considerations were included as part of the design of this study.

Data Safety Monitoring Plan

Monitoring of Adverse Events: While levetiracetam is not used in treating Alzheimer's disease, it is widely used in the treatment of epilepsy, including epilepsy that develops in patients with Alzheimer's disease. We will be using a single dose, so the risk of side effects is low.

Participants will complete the side effects questionnaire prior to and after every session in order to evaluate side effects.

The occurrence of any unexpected undesirable side effect will result in holding the trial until communication with the IRB, the CRC administrative staff, and the Research Subject Advocate

has taken place, and the risk for participants reassessed. Participation in the study for any given participant will stop in the event of any unexpected side effects or any cognitive deterioration as measured by the serial assessments described above.

Reporting of Adverse Events: All adverse events will be reported and reviewed every week according to laboratory policies. Information about all adverse events relating to this study will be collected and reported on the attached Report of Adverse Event Form. Any adverse event occurring in participants after they sign the consent form and until two weeks after the trial will be reported according to the following guidelines:

- (1) All fatal, life-threatening or serious adverse events will be reported verbally ([name]) and faxed ([name]) to the CRC RSSO Director and the CCI within 24 hours.
- (2) Unexpected serious adverse events will be reported verbally in real time to the CCI and the CRC RSSO Director.
- (3) Unexpected moderate adverse events will be reported in writing to the CCI and the CRC RSSO Director within 10 days of occurrence or recognition.

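### Both primary outcomes rest on a repeated measures ANOVA with no rule for participants who stop early, while the cognitive stopping rule names no test or threshold; a mixed model on all attended sessions is a cheap remedy

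*Combined protocol and SAP*

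**What the plan says.** B8, Monitoring of Adverse Events: participation "will stop in the event of any unexpected side effects or any cognitive deterioration as measured by the serial assessments described above". No instrument, comparator or size of decline follows. Three repeated assessments could be meant:

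- The side effects questionnaire, in the same part of B8: "Participants will complete the side effects questionnaire prior to and after every session".
- The neurological exam (B3.A.5.j), "Neurological exam: mental status, cranial nerves, motor system" and so on. The Study Plan (B3.A.6) lists it at screening and ahead of the infusion at visits 1-3.
- The cognitive battery, given after dosing (B1): "After drug administration, repeat EEG, ASL-MRI perfusion imaging, and behavioral testing will be conducted". It contains a primary outcome (B3.A.5.o): "The primary endpoint for memory testing will be the free recall score from the Free and Cued Selective Reminding Test".

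The MMSE is scheduled at screening only.

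Sessions can also be lost in other ways. The same B8 sentence stops anyone with an unexpected side effect, and B6 states: "Participants will be reminded at the start of each session that they may discontinue at any time".

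B3.B plans repeated measures ANOVA for memory and for hippocampal perfusion. The secondary whole-brain analysis uses a random effects model. Nothing is said about missed sessions, early stoppers or replacement. The margin from 25 screened to 20 randomised covers screening. The one sentence on keeping data (B8) concerns revoked privacy authorisation and is not an analysis rule.

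**The concern.** The two gaps compound each other. The first stops people on a criterion that is not defined. The second leaves open what happens to the sessions they have already completed. Each session takes 5-7 hours and includes an infusion, EEG and MRI, and there are only 20 subjects. Under classical repeated measures ANOVA, someone who completes two sessions and then stops contributes nothing.

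If the stopping criterion were the battery itself, ordinary session-to-session noise in a primary endpoint could end participation. The first available comparison would be session 2 with session 1, taken under different treatments. Precision is at stake and, for some triggers, so is the size of the estimated memory effect.

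**Working it through.** **1. The plan's own figure.** From the table in B2, the effect is 0.96 - 0.77 = 0.19. The SD is sqrt((0.29² + 0.17²)/2) = 0.238, so the ratio is 0.80. For two groups of 20 at two-sided 0.05 (alpha is assumed; the plan states none), power is Φ(0.80 × sqrt(20/2) - 1.96) = Φ(0.57), or 0.715. The plan states 72%. That figure treats the comparison as two independent groups and makes no allowance for early stopping.

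**2. How many could stop if any fall in free recall counts.** In within-subject SD units the session 2 minus session 1 difference has SD √2. With a practice gain g and no drug effect on memory, P(stop) = Φ(-g/√2). For g = 0, 0.5 and 1 this is 50%, 36% and 24%. With integer scores and a within-subject SD of 2-5 points, ties lower it to 43-47%, 30-34% and 19-22%. A fall at session 3 costs nothing.

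**3. Sessions lost.** At 50% stopped, 60 - 10 = 50 sessions are attended and complete-case ANOVA uses 10 × 3 = 30. At 24% (4.8 people), about 55 are attended and 15.2 × 3 ≈ 46 are used.

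**4. Perfusion power at the planning effect.** The within-subject SD is the total SD × sqrt(1 - ρ). The effect of 0.80 total SD therefore becomes 0.955, 1.13 and 1.46 within-subject SD at ρ = 0.3, 0.5 and 0.7. As a closed-form check at ρ = 0.3 with no stops, the contrast of both doses pooled against placebo has noncentrality 0.955/sqrt(1.5/20) = 3.49 on 38 df, which gives 93%.

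Simulation settings: n = 20; six sequences in blocks of six; equal effect of both doses; memory effect 0.78 within-subject SD; within-subject memory-perfusion correlation -0.5; stop after session 2 if memory is below session 1; 3,000 replicates (Monte Carlo SE at most 0.9 points). Mean completers were 10.0, 12.5 and 14.8 at practice gain 0, 0.5 and 1. Pooled-dose contrast:

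| ρ | No stops | Complete-case ANOVA, g = 0 / 0.5 / 1 | Mixed model, g = 0 / 0.5 / 1 |
|---|---|---|---|
| 0.3 | 93% | 62 / 72 / 79% | 84 / 88 / 89% |
| 0.5 | 98% | 77 / 85 / 90% | 94 / 95 / 96% |
| 0.7 | nearly 100% | 92 / 98 / 99% | 99 / 100 / 100% |

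Repeat runs moved the ρ = 0.3 complete-case entries by one or two points, hence 62-80%.

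The planned analysis has a three-level session factor, so its overall test is the 2-df F test. With no practice gain, at ρ = 0.3/0.5/0.7, its power is 86/95/100% with no stops, 50/66/86% complete-case and 73/87/98% with the mixed model.

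The mixed model's gain comes from the kept sessions: without a period term and with no practice gain, the pooled contrast still has 85/94/99%.

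**5. Bias.** When any fall counts, complete-case estimates are 0.77-0.80 for a true memory effect of 0.78, and -0.73 to -0.79 for a true perfusion effect of -0.78. With larger triggers and no practice gain, the memory estimate falls:

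- 0.25 within-subject SD trigger: 0.74, which is 5% low
- 0.5 SD: 0.71, 9% low
- 1 SD: 0.68, 13% low
- 1.5 SD: 0.67-0.68, 13-14% low

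With no true effect there is no bias, and the completers' type I error was 0.027-0.050. The mixed model returned the true memory effect, with type I error of 4-5%.

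**6. If few stop.** With an assumed 5% stopped (n = 19), power at ρ = 0.3/0.5/0.7 is 91/97/100%, against 93/98/100% with n = 20.

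**The case against.** The strongest reply is that the rule is a safety provision, placed under adverse event monitoring next to the side effects questionnaire. No investigator would read it as ending participation over a one-point fall in free recall, since that would remove up to half the cohort on noise. On an ordinary clinical reading, step 6 shows almost no loss. The plan also expects the within-subject design to reduce variance markedly, which points towards the ρ = 0.7 row. This is a pilot, and complete-case deletion is inferred from the classical form of the ANOVA; the protocol does not specify it.

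Most of this stands. The battery reading is the least plausible of the three, and every figure in steps 2 to 5 is conditional on it. What remains is that the plan provides for early stopping by several routes and has no rule for partial data in either primary analysis, whichever reading is meant.

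A reader might infer that the rule will cost half the subjects, or that it could manufacture a drug effect. The documents do not support either. They do not say that battery scores trigger stopping, and under no drug effect the check finds neither bias nor inflated type I error. The opposite inference, that bias can be ignored, is also too strong: with no threshold stated, triggers of 0.25-1.5 SD are just as open, and they attenuate the memory effect.

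**Conclusion.** The point holds as a cheap improvement to the analysis, together with a needed clarification of the stopping rule. It is not a design flaw. The size depends on what the rule means: slight if stops are few; moderate at ρ = 0.3-0.5 if any fall in memory score stops participation; small for the pooled contrast at ρ = 0.7.

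The loss is large only for a more modest effect. At 0.78 within-subject SD (0.43 total SD at ρ = 0.69) with no practice gain, perfusion power is 79% with no stops, 47% complete-case and 65% with the mixed model. That effect is illustrative and is not in the documents. The attenuation in step 5 runs towards zero, so it would understate a real memory benefit.

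Within-subject correlation, practice gain, memory effect, memory-perfusion correlation and trigger size are all assumptions. Confidence in the numbers is medium. That the two rules are missing is clear from the text.

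**What to change.** **Analysis.** Analyse both primary outcomes with a likelihood-based mixed model, with dose and period fixed and subject random, on every attended session. Tabulate stops by sequence and last dose. As a sensitivity check, model memory and perfusion jointly. Do not adjust perfusion for the post-dose memory score: that removes part of the drug effect (in the simulation -0.78 became -0.49 to -0.51). The cost is slightly more analysis work and one extra table, with no new visits, tests or patients. It is worth doing even if the stopping wording stays.

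**Stopping rule.** The investigators should name the assessment and the size of decline that stop a participant, keep a post-dose safety check, and keep the investigator's right to stop anyone.

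Resting the cognitive stop on the pre-dose mental status exam alone would not do. Sessions are at least 7 days apart and the half-life is 10-11 hours, so at least 168/11 ≈ 15 half-lives have passed by then, and acute post-dose harm would go unseen. Borrowing the 'moderate' level from adverse event reporting ("Unexpected moderate adverse events will be reported in writing to the CCI and the CRC RSSO Director") would not help either, because the protocol does not define it. Any threshold looser than the present wording trades away some caution, and that choice belongs to the investigators.

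If they choose a numeric threshold on a battery test, it should be paired with the mixed model. A fall of 1.645 SD of the difference stops about 5% by noise. Under complete-case ANOVA it gives a memory effect of 0.71-0.74 for a true 0.78 (practice gain 0-0.5), while the mixed model gives 0.78.
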